4.4 Safety assessments

All safety assessments analyses will be performed based on FAS.

• Laboratory assessments (Hematology, Chemistry, Urinalysis)

Value and change from baseline on continuous data (test results) will be summarized using descriptive statistics at each scheduled time point. Shift tables for evaluation of laboratory parameters from baseline to each scheduled time point will be provided. All laboratory assessments will be listed. Clinically significant laboratory results will be flagged, listed and summarized separately.

• Physical Examination、ECG and Vital Signs

Vital Sign test value at each visit and change from baseline values will be summarized using descriptive statistics. Shift tables for evaluation from baseline to each scheduled time point will be provided by each parameter. All physical examination, ECG and vital signs results will be listed. Clinically significant results will be flagged, and listed separately.

• Eastern Cooperative Oncology Group (ECOG)

The ECOG performance status scale (Grade 0-5) will be summarised by the frequency counts and percentage for each grade at each time point. The Shift tables will be performed based on Baseline (Visit 1) and other time points. All information about ECOG will be listed for each subject.

Above analyses will be performed based on FAS.

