4.3 Treatment period

Descriptions of the procedures for this period are included in the Study Plan with exceptions of the following specific requirements for the treatment period:

All visits must occur within \pm 5 days starting at visit 2 from the scheduled date. All assessments will be performed on the day of the specified visit unless a time window is specified.

ECOG performance status and weight will be performed at Day 1, Day 85, or Day 169/at end of treatment visit.

Haematology and Serum chemistry will be tested at Day 1, Day 85, or Day 169/at end of treatment visit. Additional monitoring for haematology and serum chemistry will be provided as clinically indicated.

Serum PSA level and testosterone level will be collected at Day 1, Day 85 or Day 169/at end of treatment visit.

Assessment of subject's eligibility for radical prostatectomy will be performed in all enrolled subjects by investigators at Day 169/at end of treatment visit as well as blood sample for germline HRR mutation testing of all enrolled subjects will be collected. If scheduled study assessments cannot be obtained because of a holiday, these assessments should be obtained at the soonest following date, unless the soonest following date is not more than 2 days away from the evaluation time of other planned studies.

If the information as the ECOG performance status, haematology, serum chemistry, serum PSA, testosterone, concomitant medications has been collected within one week prior to the end of treatment visit, it will no more be collected, unless it is considered by the investigator that relevant information will be significantly changed in a short period.

Investigators can suggest patients to take regular serum transaminase test in the outpatient department of hospital for the first four months of treatment with Casodex and then periodically, followed clinical practice or as clinical indicated. Management of abnormal results of serum transaminase that causally related to Casodex please follow the guidance in Section 6.10.

If the dose of Zoladex (Goserellin acetate implant) is delayed by more than 7 days during ontreatment period, early termination of study treatment will be considered. If Zoladex is permanently discontinued, Casodex should be permanently discontinued.

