6.4.6 Adverse events based on examinations and tests

The results from protocol mandated laboratory tests and vital signs will be summarised in the CSR. Deterioration as compared to baseline in protocol-mandated laboratory values, vital signs and ECG abnormalities should therefore only be reported as AEs if they fulfil any of the SAE criteria or are the reason for discontinuation/interruption/dose reduction of treatment with the IP, or if the investigator believes that the abnormality should be reported as an AE.

If deterioration in a laboratory value/vital sign is associated with clinical signs and symptoms, the sign or symptom will be reported as an AE and the associated laboratory result/vital sign will be considered as additional information. Wherever possible the reporting Investigator uses the clinical, rather than the laboratory term (e.g., anaemia versus low haemoglobin value). In

the absence of clinical signs or symptoms, clinically relevant deteriorations in non-mandated parameters should be reported as AE(s).

Deterioration of a laboratory value, which is unequivocally due to disease progression, should not be reported as an AE/SAE.

Any new or aggravated clinically relevant abnormal medical finding at a physical examination as compared with the baseline assessment will be reported as an AE.

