6.10 Management of IP related toxicities

Laboratory abnormalities including elevated AST, ALT, bilirubin, BUN (blood urea nitrogen), and creatinine and decreased hemoglobin and white cell count have been reported in both Casodex-LHRH analogue treated and flutamide-LHRH analogue treated subjects.

Rare cases of death or hospitalization due to severe liver injury have been reported postmarketing in association with the use of Casodex. Hepatotoxicity in these reports generally occurred within the first three to four months of treatment. Hepatitis or marked increases in liver enzymes leading to drug discontinuation occurred in approximately 1% of Casodex patients in controlled clinical trials.

Serum transaminase levels should be measured prior to starting treatment with Casodex, at regular intervals for the first four months of treatment, and periodically thereafter. If clinical symptoms or signs suggestive of liver dysfunction occur (e.g., nausea, vomiting, abdominal pain, fatigue, anorexia, "flu-like" symptoms, dark urine, jaundice, or right upper quadrant tenderness), the serum transaminases, in particular the serum ALT, should be measured immediately. If at any time a subject has jaundice, or their ALT rises above two times the upper limit of normal, Casodex should be immediately discontinued with close follow-up of liver function.

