4.3.7.4 Adverse events(AEs)

Treatment-emergent AEs (TEAEs) are defined as the AEs occurring on or after the first dosing of study drug and up to 4 weeks after discontinuation of study drug. All AEs will be listed and summarized. See Appendix 1 for handling of partial dates for AEs, in the case where it is not possible to define TEAEs, the AEs will be identified as TEAEs.

AEs will be categorized into one or more of the following categories depending on the type of events reported:

- AEs
- SAEs
- Treatment-emergent AEs,
- Drug-related AEs (Zoladex related, Casodex related)
- Drug-related SAEs
- AEs leading to study drug discontinuation
- AEs with an outcome of death
- AEs of CTCAE Grade 3 or higher

An overall summary of the number and percentage of subjects in each category will be presented, as will an overall summary of the number of events in each category.

The number and percentage of subjects with TEAEs in each category above will be summarized and events in each category will be further summarized by MedDRA SOC and PT.

All related information (such as SOC/PT, CTCAE Grade, outcome, etc.) about adverse event will be listed for each subject and each term, based on following category: Deaths, SAEs and AEs. Above analyses will be performed based on FAS.

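### Protocol 4.3 narrows the cross-reference to the unconditional ALT stop rule in 6.10, and SAP 4.4 has no row at 2 x ULN, so a crossing judged unrelated could appear only in a listing

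*SAP*

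**What the plan says.** **The stop rule.** Protocol 6.10, headed "Management of IP related toxicities", says that if at any time a subject has jaundice or "their ALT rises above two times the upper limit of normal, Casodex should be immediately discontinued". The sentence carries no causality condition.

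**The reference to it.** Protocol 4.3, which governs the treatment period, first says that investigators may suggest outpatient transaminase tests. It then says "Management of abnormal results of serum transaminase that causally related to Casodex please follow the guidance in Section 6.10".

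**When a laboratory change becomes an AE.** Under protocol 6.4.6, deterioration in a mandated laboratory value is reported as an AE only if it meets an SAE criterion, is the reason for stopping, interrupting or reducing study drug, or "if the investigator believes that the abnormality should be reported as an AE".

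**What is tabulated.** SAP 4.4 says "Value and change from baseline on continuous data (test results) will be summarized using descriptive statistics at each scheduled time point". It also plans shift tables at scheduled time points and a listing of all laboratory results. It adds "Clinically significant laboratory results will be flagged, listed and summarized separately", for which neither document gives a criterion. SAP 4.3.7.4 has a category for "AEs leading to study drug discontinuation". SAP 2.2 counts subjects with protocol deviations. No planned output counts subjects with ALT above 2 x ULN.

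**The concern.** The two protocol sections can be read as different rules for the same laboratory value. One site follows the words of 6.10, stops Casodex and so generates an AE leading to discontinuation. Another relies on 4.3, judges the rise unrelated, continues dosing and sees no deviation to report. The first stake is subject protection, because the same ALT result could lead to different management depending on the section followed. The second is reporting. Safety of the combination is a secondary objective, and 6.10 describes rare deaths and hospitalisations from severe liver injury with Casodex. The ALT threshold set in response is not used in any planned table.

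**Working it through.** The plan has no figure of its own on this point, so the check is mainly a tracing of the text.

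**1. Trace a crossing under each reading.** Suppose a subject on Casodex has ALT above 2 x ULN.

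| Planned output | 6.10 read as unconditional | 4.3 read as limiting 6.10; rise judged unrelated |
|---|---|---|
| Casodex | Stopped | May continue |
| AE under protocol 6.4.6 | Yes, as the reason for stopping | Only if an SAE criterion is met, dosing is interrupted or reduced, or the investigator chooses to report it |
| AE leading to discontinuation (SAP 4.3.7.4) | Counted | Not counted |
| Deviation (SAP 2.2) | A recognised failure to stop is counted | The site sees none |
| Clinically significant summary (SAP 4.4) | If flagged | If flagged |
| By-visit statistics and shift tables | If at a scheduled time point | If at a scheduled time point |
| Listing | Yes, if captured | Yes, if captured |

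The gap lies in the right-hand column. It needs four things together: the rise is judged unrelated and Casodex continues, the result comes from an unscheduled test, it is not flagged as clinically significant, and it is not reported as an AE.

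**2. How likely is an unscheduled finding?** Chemistry on treatment is scheduled at Day 1, Day 85 and Day 169 or end of treatment. Protocol 6.10 says hepatotoxicity generally occurred in the first three to four months. After Day 1, only the Day 85 draw falls in that period. Other tests in those months are ones the investigator may suggest, so an unscheduled test is a plausible route of detection.

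**3. How likely is a judgement of unrelated?** Appendix A says a reasonable possibility could be considered to exist when one or more listed factors are present. These include time course and consistency with the known drug profile. Ambiguous cases count as related. Protocol 6.10 itself names raised ALT as reported with Casodex. A rise on treatment will therefore usually qualify as related unless another cause is more likely.

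**4. What size can be given?** The documents state no rate for ALT above 2 x ULN and no share judged unrelated. The one liver figure is "Hepatitis or marked increases in liver enzymes leading to drug discontinuation occurred in approximately 1% of Casodex patients in controlled clinical trials". Those events led to discontinuation, which the plan already counts, so this rate does not measure the gap. What can be shown is the effect of one omission, with all 104 planned subjects in the FAS and exact (Clopper-Pearson) limits:

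- One crossing counted: 1/104 = 0.96%, 95% CI 0.02% to 5.24%.
- The same crossing missed: 0/104 = 0%, upper limit 1 - 0.025^(1/104) = 3.48%.

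**5. Is the design affected?** Protocol 8.2 gives a half-width of 6.1% for a 90% rate with 10% dropout. With 104 x 0.9 = 93.6 evaluable subjects, 1.96 x sqrt(0.9 x 0.1 / 93.6) = 6.08%, which reproduces it. No ALT result enters that calculation.

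**The case against.** The strongest reply is that 6.10 stands on its own. Its sentence applies at any time and without condition, a section heading is not a condition, and 4.3 nowhere tells a site to keep giving Casodex. On that view 4.3 is a loosely worded pointer, every crossing should lead to a stop, and the planned outputs count both the stop and any recognised failure to stop. This largely stands. A reader might infer that the protocol permits continuation after an unrelated rise, but the text does not say so. What remains is that 4.3 invites that reading, and correcting it costs almost nothing.

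A reader might also infer that every planned view of an ALT crossing depends on an investigator's opinion. The documents do not support that. The by-visit statistics include the maximum (SAP 4.1), and the shift tables use measured values without a causality or AE filter. The shift categories are undefined, so it cannot be said that they ignore multiples of ULN. SAP 4.3.5.1 also counts subjects with a dose interruption or reduction.

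Finally, a threshold row can be called a matter of table design in a descriptive study where all laboratory results are listed. That is fair, and it is why the SAP part is only a minor addition.

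**Conclusion.** The inconsistency between protocol 4.3 and 6.10 is real and should be removed. Its reporting consequence is narrow: a crossing that meets all four conditions in step 1 of the working is listed but not counted. Appendix A should make the first condition uncommon. A reader might infer that the trial will materially understate liver toxicity, but the documents provide no rate from which to claim that. The 1/104 against 0/104 comparison shows only what one omission would do.

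The conclusion assumes that some site would rely on the wording of 4.3 and that the unscheduled result reaches the database. If outpatient results are not captured, the value would not be in the listing either, and the documents do not settle this. The primary endpoint, the sample size of 104 and the 6.1% precision are untouched. Severity is minor.

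**What to change.** 1. **Protocol 4.3.** Delete the five words that limit the cross-reference to results causally related to Casodex, so that the 6.10 stop rule applies whatever the causality. Do not resolve the conflict by adding a causality condition to 6.10, because that would weaken a safety rule.
2. **SAP 4.4, as a minor addition.** Add one FAS row: number, percentage and Clopper-Pearson 95% CI of subjects with any recorded ALT above 2 x local ULN after first dose and up to the end-of-treatment visit. Include unscheduled values where captured. Split the row by Casodex stopped or continued, and show subjects already above 2 x ULN at baseline separately.
3. **Causality.** Do not split the row by investigator causality. Protocol 6.4.3 and 6.4.4 collect causality per AE, so none exists for a crossing never reported as one. Show it in the listing only where an AE was reported.

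The cost is one phrase in the protocol and one table row, with no new blood draws or subjects. Local ULN must be entered if the eCRF does not hold it. The row describes recorded results only and does not estimate the true rate of crossings.

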4.5 Exploratory endpoints

All the subjects receiving surgical treatment will receive germline and tumor tissue gene test after surgery. The frequency counts and percentage of subjects with harmful t-HRRm detected in tumor tissue gene test or germline homologous recombination repair mutation will be summarized respectively.

Above analyses will be performed based on RPAS.

5. INTERIM ANALYSES

No interim analyses are planned.

6. CHANGES OF ANALYSIS FROM PROTOCOL

NA

7. APPENDIX 1: PARTIAL DATE CONVENTIONS

Imputed dates will NOT be presented in the listings.

Algorithm for Treatment-emergent Adverse Events:

START DATE	STOP DATE	ACTION
Known	Known/Partial/Missing	If start date < study treatment start date, then not TEAE
		If start date >= study treatment start date, then TEAE
Partial, but known	Known/Partial/Missing	Not TEAE
components show that it cannot be on or after study treatment start date	, , , , , , , , , , , , , , , , , , , ,	
Partial, could be on or after study treatment start date	Known/ Partial/Missing	Impute stop date as latest possible date (i.e. last day of month if day unknown or 31st December if day and month are unknown), if partial or missing date exist.
		If stop date < study treatment start date, then not TEAE
		If stop date >= study treatment start date, then TEAE
Missing	Known/ Partial	Impute stop date as latest possible date (i.e. last day of month if day unknown or 31st December if day and month are unknown), if partial or missing date exist.
		If stop date < study treatment start date, then not TEAE
		If stop date >= study treatment start date, then TEAE
	Missing	Assumed TEAE

Algorithm for Prior / Concomitant Medications:

START DATE	STOP DATE	ACTION
Known	Known	If stop date < study treatment start date, assign as prior If stop date >= study treatment start date and start date <= end of treatment+3 months, assign as concomitant If start date > end of treatment+3 months, assign as post study
	Partial	Impute stop date as latest possible date (i.e. last day of month if day unknown or 31st December if day and month are unknown), then: If stop date < study treatment start date, assign as prior
		If stop date >= study treatment start date and start date <= end of treatment+3 months, assign as concomitant If start date > end of treatment+3 months, assign as post treatment
	Missing	If start date > end of treatment+3 months, assign as post treatment If start date > end of treatment+3 months, assign as post treatment If start date > end of treatment+3 months, assign as post treatment
Partial	Known	Impute start date as earliest possible date (i.e. first day of month if day unknown or 1st January if day and month are unknown), then: If stop date < study treatment start date, assign as prior If stop date >= study treatment start date and start date <= end of treatment+3 months, assign as concomitant If start date > end of treatment+3 months, assign as post treatment
	Partial	Impute start date as earliest possible date (i.e. first day of month if day unknown or 1st January if day and month are unknown) and impute stop date as latest possible date (i.e. last day of month if day unknown or 31st December if day and month are unknown), then: If stop date < study treatment start date, assign as prior If stop date >= study treatment start date and start date <= end of treatment+3 months, assign as concomitant If start date > end of treatment+3 months, assign as post treatment
	Missing	Impute start date as earliest possible date (i.e. first day of month if day unknown or 1st January if day and month are unknown), then: If start date <= end of treatment+3 months, assign as concomitant If start date > end of treatment+3 months, assign as post treatment
Missing	Known	If stop date < study treatment start date, assign as prior If stop date >= study treatment start date, assign as concomitant Cannot be assigned as 'post treatment'
	Partial	Impute stop date as latest possible date (i.e. last day of month if day unknown or 31st December if day and month are unknown), then: If stop date < study treatment start date, assign as prior If stop date >= study treatment start date, assign as concomitant Cannot be assigned as 'post treatment'
	Missing	Assign as concomitant
